7.4.1 Visit Procedures

- Patients will be asked to arrive at the visit at least 1 hour in advance of the start of the BP having fasted since 12:00 AM the night before (treatment with simple carbohydrate of up to 30 g for a low is allowed). If the patient is not fasted, the visit will be rescheduled within the visit window. If BG is >250 mg/dL, the visit will be rescheduled within the visit window. If BG is <50 mg/dL, treatment with simple carbohydrate is allowed. If the patient experiences persistent hypoglycemia, the visit will be rescheduled within the visit window. If the visit needs to be rescheduled due to hypoglycemia or hyperglycemia, trial staff will assist the patient with insulin or medication adjustments to address glycemic control. The patient will be instructed to contact trial staff later in the day if his or her BG remains uncontrolled.
- Upon arrival to the visit, the patient's weight and vital signs including body temperature and blood pressure will be documented.
- Patient reports of symptoms, any other complaints, and AEs will be reviewed.
- Concomitant medications will be recorded.
- Chemistry and hematology samples will be collected at visit start (see [Appendix B](#)).
- ADA samples will be collected before the start of dosing (Visit 3 only).
- A 12-lead ECG will be performed.
- A urine HCG pregnancy test will be performed in female patients of childbearing potential. If the test is positive, the patient will be informed of the result and the visit will be ended.
- Patients will complete a baseline survey about their attitudes and experience with their usual diabetes care.
- An intravenous (IV) catheter will be placed for blood sampling.

Clinical Trial Protocol
ZP4207-16051

Version number: 3.0
Amendment 2.0
Date: 03 August 2016

- Trial staff will assist the patient to calibrate their CGM, review the trial procedures again and assist with the setup of the BP system, including inserting and priming infusion sets.
- The control algorithm will be initialized only with the patient's weight. Diagnostics will be performed to ensure that the CGM device is appropriately calibrated and that all of the components of the BP systems are in working order.
- The basal rate of the patient's own insulin infusion pump will be changed to be 2-fold higher than weighted mean of the basal rate during the trial period. This is intended to increase the usage of glucagon during the treatment visit.
- The patients will continue to wear their own infusion pump infusing at the temporary 2-fold basal rate throughout the visit until the start of the structured exercise period, in addition to the BP.
- The staff will start the BP as close as possible to a minute divisible by 5 minutes (i.e., on a 5-minute mark). The starting time will be considered Hour 0.
- Additional calibrations will be performed at any of the BG checks throughout the day if the CGM value does not meet the ISO standard (<15 mg/dL difference for BG values <75 mg/dL; <20% absolute difference for BG values >75 mg/dL) at the time of the BG measurement AND it is a good time to calibrate (the CGM trend arrow is flat and there has been no carbohydrate intake in the last 30 minutes or glucagon boluses in the last 15 minutes).
- Blood samples will be taken from the IV at least hourly and processed for plasma ZP4207/glucagon. If BG is <150 mg/dL, more frequent samples for plasma ZP4207/glucagon may be drawn at the discretion of the Investigator. The actual time of sampling will be recorded in the eCRF.
- Plasma glucose samples will be taken from the IV at least hourly in parallel with ZP4207/glucagon exposure sampling and measured using the YSI 2300 STAT Plus. If the YSI 2300 STAT Plus and/or IV fails, the Nova StatStrip Xpress will be used for glucose measurements. If BG is <150 mg/dL, then sampling will be every 30 minutes. If BG is <100 mg/dL, then sampling will be every 20 minutes. If BG is <80 mg/dL, then sampling will be every 10 minutes. The actual time of sampling will be recorded in the eCRF.
- Patients will be asked to rate any nausea and/or infusion site pain on 10 cm visual analog scales (VAS) at the beginning of the visit once the infusion sites have been placed but no drug has yet been administered, then approximately at the top of every hour during the visit, and at the end of the visit. Trial staff will also evaluate their infusion sites to document any erythema or edema at the same times. If moderate or severe pain is reported or swelling or redness occurs at the infusion site, the infusion site will be replaced in a different location. If moderate or severe pain, swelling, or redness continues at the old site for more than 30 minutes after the infusion site is removed, or if moderate or severe pain, swelling, or redness occurs at the new site, all infusion sites will be removed and the patient will be discontinued from the study. Any such symptoms will be followed until resolution.
- From the start of closed loop control until approximately Hour 3, the patients will continue to fast.
- Between approximately Hour 3 and Hour 4, patients will be provided with a lunch meal of their choice in the Diabetes Research Center from a menu of choices from nearby restaurants. They will be asked to choose a meal that is a "typical meal" for them. The content of their meal will not be restricted in any way, with the exception that the

Clinical Trial Protocol
ZP4207-16051

Version number: 3.0
Amendment 2.0
Date: 03 August 2016

number of carbohydrates should be in the “typical” range for them at lunch, and that they must eat the same meal at the same time during both visits.

- At approximately 15 minutes before the meal, patients will administer a bolus for the meal with their own insulin pump based on the carbohydrate count for the meal.
- After lunch is completed, the patients will not be allowed any carbohydrate intake (non-caloric drinks will be permitted) until the trial is completed (except as necessary to treat hypoglycemia), to allow the BP to control the post-prandial BG without further interruption.
- Between approximately Hour 6 and Hour 7, the patients will start a period of structured exercise.
- At the start of the exercise period, patients will restore their normal basal insulin profile so that they will not have elevated insulin levels at the end of the study period when they are to transition back to their usual care.
- Patients will exercise on a stationary bike with a heart rate from 120-140 beats per minute for a total of 4,000 heart beats (approximately 30 minutes). Patients will rate their exercise intensity using the Borg scale every 5 minutes, with the target intensity level between 12 and 14. Heart rate will be measured every 5 minutes.
- BG measurements will be obtained off of the IV line every 10 minutes. If BG is <80 mg/dL, BG measurements will be obtained off of the IV line every 5 minutes.
 - Carbohydrates will be given for any BG <50 mg/dL according to the following protocol: Dextrose (g) = BSA (m²)/[1.7 m² (women) or 1.9 m² (men)] *15 g.
 - Repeat treatments will be given at 15-minute intervals as long as BG remains <50 mg/dL.
- If there is an interruption in the Dexcom CGM output, trial staff will assist the patient in recovering CGM data streaming. If this requires replacement of the CGM sensor, BGs will be checked every 10 minutes (every 5 minutes if BG is <80 mg/dL) using blood from the IV until the CGM is able to be calibrated again. These BGs will be entered into the BP, which will treat them as CGM values and dose insulin and/or glucagon appropriately.
- If there is a complete failure of the BP operation, patients will take over their own BG control using their personal insulin pump until the BP can be brought back online. If BP control cannot be promptly resumed (e.g., within 30 minutes), the patient may be asked to repeat that trial day once.
- Patients may choose to withdraw from the trial at any time. If they withdraw from the trial, they should alert a provider immediately.
- Just prior to the end of the study visit, vital signs including body temperature and blood pressure will be obtained and a 12-lead ECG will be performed.
- After approximately Hour 8, but not earlier than at least 60 minutes after end of exercise, the BP will be stopped and the patient will continue with their personal insulin pump.

Clinical Trial Protocol
ZP4207-16051

Version number: 3.0
Amendment 2.0
Date: 03 August 2016

- If the patient experiences seizure or unconsciousness, persistent nausea or vomiting, diabetic ketoacidosis, persistent hyperglycemia with ketonemia, hemodynamic changes such as hypotension, or other medically significant findings, a longer observation period at the trial site may be necessary until the patient is considered stable for discharge. If the Investigator or trial staff determines that the patient requires further observation or treatment, the patient may be transferred to the emergency room for additional monitoring and/or medical care. At discharge, patients will be provided with any necessary instructions concerning personal insulin pump usage, food intake, and driving arrangements.
- The maximum amount of blood loss per study visit will be approximately 230 mL. The total blood loss for the entire study will be up to 460 mL.
- Patients will answer questionnaires (see [Appendix C](#)).
- Chemistry and hematology samples will be collected at visit end (see [Appendix B](#)).
- The BP and glucose meters will be collected and downloaded.
- A trial MD will review the last several hours of insulin and glucagon dosing and assist the patient in resuming their usual diabetes care. A longer observation period at the trial site may be necessary. Patients will be instructed to call trial staff with any questions, issues, or concerns.

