7.4.4 Response to Hyperglycemia

- Trial staff will check the infusion site, BP, and insulin pump for normal operation any time BG is >300 mg/dL. If there is any suspicion of infusion set malfunction, the site should be replaced. Trial staff will check the BP for any malfunction and correct any problems that are found. If the BG remains >300 mg/dL for 2 hours despite troubleshooting, blood ketones will be measured. If the blood ketone result is >1.5 mmol/L, the visit will be stopped and rescheduled. The patient will be provided with insulin and a syringe to give an injection based on their correction factor.
- If a patient experiences diabetic ketoacidosis, his or her participation in the trial will be discontinued.
- If no correctable fault is found, but there is doubt regarding the correct function of the BP system, the treatment visit may be stopped and the visit rescheduled.

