7.6 Follow-up Visit (Visit 6)

Patients will return for a Follow-up Visit 25 days \pm 4 days following the last day of dosing (Visit 4), for chemistry, hematology, and ADA sampling, and a review of AEs and concomitant medications.

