 - >250 mg/dL
 - >300 mg/dL
- Number of severe hypoglycemic events (patients unable to self-treat, requiring the assistance of another person)
- Number of episodes of symptomatic hypoglycemia
- Number of carbohydrate interventions for hypoglycemia
- Total grams of carbohydrates taken for hypoglycemia
- Mean CGM glucose

Clinical Trial Protocol
ZP4207-16051

Version number: 3.0
Amendment 2.0
Date: 03 August 2016

8.2.3 **Non-glycemic**

- Glucagon/ZP4207 total delivery per kg of body mass
- Insulin total delivery per kg of body mass
- Number of unscheduled infusion set replacements
- Number of unscheduled CGM sensor changes

9 **LABORATORY ASSESSMENTS**

Descriptions of sample handling and sample processing, storage, and shipment at the site will be included in the laboratory manual.

The responsible laboratories are listed in the [address list](#).

9.1 **Safety Laboratory Assessments**

Chemistry and hematology samples will be collected at specified time points. See [Appendix A](#) for the schedule of procedures and [Appendix B](#) for a list of clinical laboratory analytes.

9.2 **Pharmacodynamic Assessments (Plasma Glucose)**

At Visit 3 and Visit 4, plasma glucose samples will be taken from the IV at least hourly in parallel with ZP4207/glucagon exposure sampling and measured using the YSI 2300 STAT Plus. If the YSI 2300 STAT Plus and/or IV fails, the Nova StatStrip Xpress will be used for glucose measurements. If BG is <150 mg/dL, then sampling will be every 30 minutes. If BG is <100 mg/dL, then sampling will be every 20 minutes. If BG is <80 mg/dL, then sampling will be every 10 minutes. The actual time of sampling will be recorded in the eCRF.

9.3 **Exposure Assessments (ZP4207 and Glucagon)**

At Visit 3 and Visit 4, ZP4207/glucagon exposure sampling will be collected at least hourly. If BG is <150 mg/dL, more frequent samples for plasma ZP4207/glucagon may be drawn at the discretion of the Investigator. The actual time of sampling will be recorded in the eCRF.

Bioanalytical Reports will be prepared.

9.4 **Anti-drug Antibody Assessments**

Blood samples (including back-up samples) for serum anti-ZP4207 and anti-glucagon antibodies will be taken at Visit 3 and the Follow-up Visit 6.

A Bioanalytical Report will be prepared.

10 **SAFETY REPORTING**

10.1 **Adverse Events**

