APPENDIX A: SCHEDULE OF PROCEDURES

Trial Visit	Visit 1 [1] Screening	Visit 2 Training	Visit 3 [2] [3] [4] [5] (1 st Treatment Visit)	Visit 4 [2] [3] [5] (2 nd Treatment Visit)	Visit 5 Phone Call [6]	Visit 6 Follow-Up [7]
Informed consent	X					
Assess/confirm eligibility	X	X				
Demographics	X					
Medical, surgical, and social history; allergies	X					
Concomitant illness	X					
Concomitant medications	X	X	X	X	X	X
Height, weight, physical examination, and vital signs including body temperature and blood pressure [8]	X		X [9]	X [9]		
12-lead ECG	X		X [10]	X [10]		
Urine HCG pregnancy test and menstrual history [11]	X		X	X		
FSH [12]	X					
Screening labs – HbA1c, optional fractionated metanephrines [13]	X					
Safety lab sampling including chemistry and hematology	X		X [10]	X [10]		X
Training on devices [14]		X				
Monitored BP use			X	X		
Plasma glucose sampling [15]			X	X		
ZP4207/glucagon exposure sampling [16]			X	X		
Nausea and infusion site pain VAS and infusion site reaction Draize scale (visit start [17], hourly, & visit end)			X	X		

Clinical Trial Protocol
ZP4207-16051

Version number: 3.0
Amendment 2.0
Date: 03 August 2016

Trial Visit	Visit 1 [1] Screening	Visit 2 Training	Visit 3 [2] [3] [4] [5] (1 st Treatment Visit)	Visit 4 [2] [3] [5] (2 nd Treatment Visit)	Visit 5 Phone Call [6]	Visit 6 Follow-Up [7]
Standardized lunch [18]			X	X		
In-clinic exercise [19]			X	X		
Questionnaires (pre & post BP)			X	X		
ADA			X [20]			X
Adverse event review			X	X	X	X

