There are four versions of the BPUOS; Adult (BPUOS-A), Youth (BPUOS-Y), Parent (BPUOS-P), and Significant Other (BPUOS-SO). This measure assessing both the benefits from, and difficulties with, use of the bionic pancreas, and consists of 38 items. A total score is generated. It is administered during and at the end of the intervention. Psychometric analysis of the BPUOS-Y is in progress using the data from the second Bionic Pancreas Camp Study in pre-adolescent children, and of the BPUOS -A is in progress using data from the Bionic Pancreas Multicenter Study in adults. Administration time is 10 minutes.

Summary of Changes, Amendment 1.0, ZP4207-16051

SUMMARY OF CHANGES DOCUMENT

PROTOCOL NUMBER ZP4207-16051

AMENDMENT NUMBER 1.0

PROTOCOL TITLE: The iLet Feasibility Trial Testing the iLet, a Fully Integrated Bihormonal Bionic Pancreas with ZP4207

AMENDMENT DATE: 28 June 2016

SUMMARY AND JUSTIFICATION OF CHANGES:

This amendment was developed to include additional safety language and measures and to improve clarity and consistency within the study protocol. The main additions include the maximum blood volume drawn per study visit and for the entire study; blood glucose (BG) checks every 30 minutes if blood glucose is <150 mg/dL; the discontinuation of patients from the trial who experience diabetic ketoacidosis; and blood ketones measurement if the BG remains >300 mg/dL for 2 hours despite troubleshooting. If the blood ketone result is >1.5 mmol/L, the visit will be stopped and rescheduled. The patient will be provided with insulin and a syringe to give an injection based on their correction factor. Blood pressure will be measured at screening as well as Visit 3 and Visit 4. The timing around visit windows was updated, and other minor edits were made throughout the protocol to provide greatly clarity and consistency. The schedule of procedures was updated to reflect the changes specified in this document.

SUMMARY OF CHANGES:

The amended protocol sections and the details of the changes are summarized in the following [sections](#). Revisions to the protocol are presented as strikethrough (ie, ~~subject~~) for text that was removed and bold (ie, **subject**) for text that was added.

Summary of Changes, Amendment 1.0, ZP4207-16051

Synopsis, Population, Page 4

Original Text:

Up to 20 adult (≥ 18 years of age) patients who already manage their T1DM using continuous subcutaneous (SC) insulin infusion pump therapy can be enrolled.

New Text:

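### The 460 mL blood-loss limit for the entire study is just two treatment visits at their maximum, with nothing left for the Visit 1 and Visit 6 draws or a repeated treatment day

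*Protocol*

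**What the plan says.** Section 7.4.1 (Visit Procedures) of version 3.0 gives two limits side by side. The first is "The maximum amount of blood loss per study visit will be approximately 230 mL". The second is "The total blood loss for the entire study will be up to 460 mL". The Summary of Changes for Amendment 1.0 names this among its main additions and describes its scope as "the maximum blood volume drawn per study visit and for the entire study".

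Blood is also drawn outside the two treatment visits:

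- Section 7.2.1 requires chemistry, hematology and HbA1c at Visit 1, with FSH and metanephrines where indicated.
- Section 7.6 brings patients back at Visit 6 "for chemistry, hematology, and ADA sampling, and a review of AEs and concomitant medications".
- Section 9.4 says of the antibody samples: "Blood samples (including back-up samples) for serum anti-ZP4207 and anti-glucagon antibodies will be taken at Visit 3 and the Follow-up Visit 6".
- In Appendix A the row "Safety lab sampling including chemistry and hematology" is marked at Visits 1, 3, 4 and 6.

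Two sections allow for an extra treatment day. Under Section 7.4.1, if control cannot be resumed promptly after a complete device failure, "the patient may be asked to repeat that trial day once". Under Section 7.4.4, if ketones exceed 1.5 mmol/L after two hours above 300 mg/dL, "the visit will be stopped and rescheduled". Section 7.4.4 also lets a visit be stopped and rescheduled when device function is in doubt.

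**The concern.** The whole-study figure is exactly twice the per-visit figure, and each patient has exactly two treatment visits. It therefore looks like a total for Visits 3 and 4 carrying a label that covers the entire study. The screening and follow-up draws are mandatory, and neither they nor an extra treatment day is excluded from the total. None of the rules on repeating or rescheduling mentions cumulative volume.

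This is a participant-safety limit on which site staff and the IRB would rely. A site that follows permitted procedures at the stated maxima would exceed it. Staff facing a failed or stopped treatment day cannot tell from the text whether another day fits within it. Heavy sampling is foreseeable: Section 7.4.1 doubles the basal insulin rate to provoke glucagon use and shortens the glucose sampling interval as glucose falls, to every 10 minutes below 80 mg/dL.

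**Working it through.** **Inputs from the protocol**

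- Maximum per study visit: about 230 mL (Section 7.4.1).
- Maximum for the entire study: 460 mL (Section 7.4.1).
- Treatment visits per patient: 2, Visits 3 and 4 (Section 7.4).
- Other visits with blood draws: Visit 1 and Visit 6 (Sections 7.2.1, 7.6 and 9.4; Appendix A). No volume is given for either.

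**Step 1. Reproduce the stated total.** 2 × 230 = 460 mL. The remainder is 460 − 460 = 0 mL. This step needs no assumption.

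**Step 2. Ordinary completer, both treatment visits at maximum.** Let v be the volume at each of Visits 1 and 6. The total is 460 + 2v. I assume v lies between 5 and 30 mL.

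- v = 5: 460 + 10 = 470 mL; 470/460 = 1.02, or 2% over.
- v = 30: 460 + 60 = 520 mL; 520/460 = 1.13, or 13% over.

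**Step 3. What each treatment visit would have to be for 460 mL to hold.** The ceiling is (460 − 2v)/2.

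- v = 5: 450/2 = 225 mL.
- v = 30: 400/2 = 200 mL.

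**Step 4. One repeated or rescheduled treatment day.** Let f be the fraction of a full day's draw taken before the failed day stopped, with the other two days at maximum. The total before Visits 1 and 6 is 460 + f × 230.

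| f | Total, mL | Over 460, mL |
|---|---|---|
| 0.25 | 517.5 | 57.5 |
| 0.50 | 575 | 115 |
| 0.75 | 632.5 | 172.5 |
| 1 (upper bound) | 690 | 230 |

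Adding Visits 1 and 6 to the upper bound gives 690 + 10 = 700 mL to 690 + 60 = 750 mL.

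**The case against.** The strongest reply is that the two limits can both hold. A whole-study ceiling need not equal the sum of every visit's maximum; if Visits 1 and 6 use some of it, the overall ceiling simply binds first and treatment-visit sampling has to give way. The device-failure repeat and the extra drug-level samples are both discretionary and can be withheld. It is true that 460 mL can be respected in practice by drawing less. But a total that equals two visit maxima to the millilitre reads as their sum, the text gives no instruction to hold the treatment visits below 230 mL, and rescheduling after high ketones is mandatory.

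A second reply is that the sentence sits under the heading for the treatment visits, where the protocol uses study and trial loosely for the treatment day, so a total over Visits 3 and 4 was meant. That may well be how the figure arose. However, the wording says the entire study, and the Amendment 1.0 summary repeats that scope. If only the treatment visits were meant, the label is wrong rather than the number.

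A third reply concerns size, and much of it stands. The Visit 1 and Visit 6 volumes are assumed, and at the low end the excess of 10 mL is within the looseness of an approximate 230 mL. The 690 to 750 mL range requires a failed day to have run to its full draw, so it is an upper bound and not an expectation.

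**Conclusion.** The point holds and is minor. The stated whole-study maximum is not the maximum that the protocol's own procedures can produce. The zero remainder and the 690 mL upper bound follow from the protocol's figures alone. The 470 to 520 mL range for an ordinary completer rests on the assumed 5 to 30 mL at each of Visits 1 and 6 and on both treatment visits reaching their maximum; a patient drawn below that may remain within 460 mL.

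The consequence is limited. The excess for an ordinary completer is probably small, Section 4.2 excludes low hemoglobin at entry, and Appendix A repeats hematology at Visits 3, 4 and 6. No endpoint or statistical analysis is affected. What remains is a safety limit that is wrong either in its number or in its label, and that gives no guidance for a repeated or rescheduled day.

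**What to change.** Either of two changes to Section 7.4.1 would settle it:

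1. Restate the whole-study maximum as the sum over Visits 1, 3, 4 and 6, and give a second figure for a patient who has a repeated or rescheduled treatment day.
2. Relabel 460 mL as the total for the two treatment visits, and make any repeat (Section 7.4.1) or reschedule (Section 7.4.4) conditional on the blood volume already drawn.

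The cost is one corrected sentence, plus one added condition on the repeat and reschedule rules under the second option. The stated total becomes larger under the first option and narrower in scope under the second.
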